6.5.2.1 Serious Adverse Event (SAE)

A Serious Adverse Event is any untoward medical occurrence that at any dose:

- Results in death;
- Is life-threatening (“life-threatening” refers to an event in which the subject was at risk of death at the time of the event; it does not refer to an event which hypothetically might have caused death if it were more severe);
- Requires inpatient hospitalization or prolongation of existing hospitalization;
- Results in a persistent or significant disability/incapacity; or
- Is a congenital anomaly/birth defect.

6.5.2.2 Adverse Device Effect (ADE)

An Adverse Device Effect is an AE related to a medical device and includes any event resulting from insufficiencies or inadequacies in the instructions for use or the

deployment, implantation, installation or malfunction of the device; any event that is the result of user error; or any potential ADE which might have occurred if suitable action had not been taken or intervention had not been made or if circumstances had been less fortunate. All AEs with a relationship to device of possibly, probably, or definitely will be considered to be ADEs.

6.5.2.3 Serious Adverse Device Effect (SADE)

A Serious Adverse Device Effect is an ADE that has resulted in any of the consequences characteristic of a SAE or might have led to any of these consequences if suitable action had not been taken; intervention had not been made or circumstances had been less fortunate. All SAEs with a relationship to device of possibly, probably, or definitely will be considered to be SADEs.

6.5.2.4 Adverse Events of Special Interest (AESI)

Some clinical concepts (including some selected individual preferred terms) have been considered as “AEs of special interest” (AESI). These AESIs will identify as a list of categories provided by the clinical team, and the study physician will review the AEs of interest and identify which preferred terms contribute to each AESI. A final review will take place prior to the database hard lock to ensure all applicable terms are captured within the categories. Preferred terms used to identify AESIs will be listed and documented prior to the database hard lock.

6.5.3 Clinical Laboratory Evaluations

A list of the specific clinical laboratory assessments completed at each study visit during the trial is listed in the protocol.

Clinical laboratory results will be converted to SI units. Change from baseline to each visit assessed and end of study will be defined using the windowing method specified in Section 6.2.2, as the visit value minus the baseline visit. Laboratory values will also be classified as normal (if value is within normal reference range) or lower/higher than normal (if value is either below or above the normal reference range).

Applicable laboratory values will also be classified using NCI CTCAE v4.0.

6.5.4 Additional Safety Variables

6.5.4.1 ECOG Performance Status

The ECOG Performance Status will be assessed according to the following categories:

Score	Characteristics
0	Asymptomatic and fully active
1	Symptomatic; fully ambulatory; restricted in physically strenuous activity
2	Symptomatic; ambulatory; capable of self-care; more than 50% of

	waking hours are spent out of bed
3	Symptomatic; limited self-care; more than 50% of waking hours are spent in bed
4	Completely disabled; no self-care; bedridden

6.5.4.2 Child-Pugh Score Status

Severity of liver disease will be assessed according to the Child-Pugh classification of Severity of Liver Disease at screening and at every 8 weeks visit.

6.5.4.3 Albumin-Bilirubin Score

Albumin-Bilirubin (ALBI) score will be assessed according to three ALBI grades in relationship to a patient's linear prediction at screening and at every 8 weeks visit. These grades are categorized as the following:

ALBI Grade	Classifier
1	Linear predictor \leq -2.60
2	$-2.60 < \text{Linear predictor} \leq -1.39$
3	Linear predictor > -1.39

The linear predictor used to compute the ALBI score for each patient is:

$(\log_{10} \text{bilirubin} \times 0.66) + (\text{albumin} \times -0.085)$,
where bilirubin is in $\mu\text{mol/L}$ and albumin is in g/L .

7 STATISTICAL METHODS

7.1 General Methodology

All statistical tests will be two-sided with a significance level of $\alpha=0.05$, unless specified otherwise, and will be performed using SAS® Version 9.1.3 or higher. Data will be summarized using descriptive statistics (number of patients, mean, standard deviation, median, minimum, and maximum) for continuous variables and using frequency and percentage for discrete variables.

Patient listings of all data from the eCRF as well as any derived variables will be presented.

7.2 Adjustments for Covariates

The following covariates will be included, one at a time together with the treatment group, in ‘univariable’ Cox regression analysis of time-to-event efficacy endpoints, including OS.

- Stratification factors
 - HCC status (unilobar vs. bilobar disease)
 - Region (North America and Europe vs Asia)
 - ECOG performance status (0 vs 1) at baseline
 - Presence or absence of branch PVT at baseline

Notes:

Stratification factors according to the master file, with any incorrect values at randomization replaced with the corrected value from the eCRF, will be used.

Patients randomized prior to the stratification change to replace HCC status with Region will have their Region covariate assigned programmatically based on site. Patients randomized after the stratification change to replace HCC status with Region will have their HCC status covariate assigned based on the eCRF collected HCC status.

- Age group (≥ 18 to < 65 years, ≥ 65 to < 75 years, and ≥ 75 years)
- Gender
- Race (White or Caucasian, Black or African American, Asian, Other [Native Hawaiian or other Pacific Islander or Native American or Alaska Native or Other])
- US and non-US region
- Duration from date of initial diagnosis of HCC to randomization (< 6 months, ≥ 6 months)
- Tumor replacement (as percentage of total liver volume) at baseline by blinded central review ($< 20\%$ or $\geq 20\%$)
- Extrahepatic disease at baseline (yes or no)
 - A patient has extrahepatic disease if the patient has extrahepatic target and/or non-target lesions (identified from target lesions and non-target lesions eCRF pages at baseline, based on a manual review of the free text

entered in the “other location, specify” and “extrahepatic location, specify” eCRF fields)

- Child-Pugh class (A5, A6, B7) at baseline
- Barcelona clinic liver cancer (BCLC) stage (B or C) at baseline. This will be derived as follows:
 - BCLC B: patients with ECOG 0, and no extrahepatic lesions, and no PVT at baseline
 - BCLC C: patients with ECOG 1, or, with extrahepatic lesions, or PVT at baseline
- HCC etiology, two categorizations will be considered for this variable
 - Categorization #1: alcoholism, hepatitis B, hepatitis C, afloxatin-contaminated food, non-alcoholic fatty liver disease, other (including unknown), based on the etiology pre-specified categories in the eCRF
 - Categorization #2: alcoholism vs. non-alcoholism; note that patients with more than one etiology are recorded under “other” and will be considered as alcoholism if one of the etiologies is alcoholism (for example, a patient with “alcoholism and hepatitis B” entered in the “other, specify” free text field will be considered into alcoholism)
- Prior oncologic treatment for HCC (yes or no)
- Bilirubin (<1 mg/dL or \geq 1 mg/dL) at baseline
- ALBI score (1 vs 2 and 3) at baseline
- AFP (<200 ng/mL or \geq 200 ng/mL) at baseline
- Maximum lesion size at baseline, defined as the longest diameter of largest target lesion at baseline according to RECIST 1.1 by investigator assessment (<7 cm or \geq 7 cm)
- Number of lesions at baseline (<3 lesions, 3-5 lesions, 6-10 lesions, $>$ 10 lesions) by blinded central review

These covariates will also be included, one at a time together with the treatment group, in a ‘univariable’ logistic regression analysis of binary efficacy endpoints.

All factors in the univariable models with a two-sided p-value $<$ 0.15 and treatment group will be included in a multivariable analysis to determine the impact of these factors. For both univariable and multivariable analyses, the overall p-value will be used for factors with $>$ 2 levels (i.e. the p-value corresponding to the Type 3 Wald chi-square statistic) rather than the p-values corresponding to each level of the factor.

For the multivariable analysis, collinearity of covariates will be assessed by the variance inflation factor (VIF)⁹, and further action will be taken if any covariate has a VIF value $>$ 10. Highly correlated covariates (i.e. with VIF $>$ 10) will be removed, one at a time, based on the descending order of their univariable p-values or clinical justification, until VIF values are \leq 10 for all covariates remaining in the multivariable model.

7.3 Handling of Dropouts or Missing Data

Dropout patients will not be replaced in this study. The handling of missing data will be discussed throughout Section 8, where relevant. Censoring for the efficacy endpoints is discussed throughout Section 8, where applicable.

7.4 Interim Analyses and Data Monitoring

An IDMC will be established to oversee the conduct of the study. The IDMC will meet periodically during the study to review enrollment, protocol deviations and safety events for the study. In addition, the IDMC will conduct and review the interim efficacy results and will make formal recommendations to the study Sponsor at the time of the interim analysis and during the conduct of the study.

After the first 20 patients in the treatment group have received TheraSphere followed by at least 2 weeks of sorafenib therapy, a feasibility safety assessment will be conducted. The IDMC will review the safety results of both the control and treatment groups in an unblinded fashion. The IDMC will take into consideration the established safety profiles of TheraSphere and sorafenib as described in the package inserts for each product as well as the published literature. The expected high rates of AEs events and death that are associated with disease progression in patients with HCC will be considered.

A consideration for stopping further enrollment to the trial may be made if there is a pattern of serious toxicity clearly related to the sequential administration of TS followed by sorafenib. Such a toxicity pattern must be clearly different from, or more severe than, what might be expected from independent administration of the products. The potential adverse impact of any such pattern of toxicity on the survival or well being of the patient should be considered in the context of the safety and outcome expectations of patients with advanced HCC.

This study uses an adaptive group sequential design with two interim analyses and one final analysis. The efficacy stopping boundaries are based on the rho family error spending function with the parameter value rho=1.5. The first interim analysis is planned at approximately, but no less than, 188 deaths, with a two-sided p-value ≤ 0.0151 allowing the study to be stopped early for efficacy. A second interim analysis is planned at approximately, but no less than, 250 deaths, with a two-sided p-value ≤ 0.0151 allowing the study to be stopped early for efficacy. If the interim analyses do not occur at exactly 188 or 250 deaths, the corresponding efficacy boundaries were to be calculated using the rho family spending function with rho=1.5.

Sample size modification is considered at the second interim analysis following the promising zone approach described in Mehta & Pocock (2011)⁴ which employs an unweighted test statistic at the final analysis as recommended by Burman & Sonesson (2006)⁵. The conditional probability boundaries for the decision rules at the second interim analysis are as follows:

- Unfavorable zone ($CP_2 < 0.42$): study size will remain at 417 deaths

- Promising zone ($0.42 \leq CP_2 < 0.8$): study size will be increased to 564 deaths
- Favorable zone ($CP_2 \geq 0.8$): study size will remain at 417 deaths

where CP_2 is defined as the conditional probability of rejecting the null hypothesis at the final analysis, given the results at the second interim analysis. Further details, including both mathematical and simulation based demonstration of type I error control, are provided in Appendix 5.

There was no sample size modification at the second interim analysis. The final analysis was originally planned when approximately, but no less than, 417 deaths have occurred. At the time of preparing this version (i.e., version 4.0) of the statistical analysis plan (SAP), 406 deaths had occurred, however, it became clear, based on the status of patients who had not yet died, that it would be unlikely to reach 417 deaths, because all patients still in follow-up on the study had already been followed up for over 40 months. Therefore, it is now planned to perform the final analysis when at least 417 deaths have occurred or on 30 April 2022, whichever comes first. If 417 deaths have not occurred on 30 April 2022 then the final analysis will be performed with the number of deaths at that time.

The boundary for the final analysis will be adjusted based on the first and second interim analyses and the actual number of deaths at the final analysis. The actual number of deaths for the first and second interim analyses were 205 and 257, respectively. However, at the first interim analysis, the efficacy boundary was inadvertently not recalculated based on the actual number of 205 deaths, and instead the p-value scale boundary stated in the SAP, based on the planned number of 188 deaths, was used. The p-value scale boundary at the second interim analysis was based on the planned number of 188 deaths at the first interim analysis, the actual number of 257 deaths at the second interim analysis and the planned final number of 417 deaths. Therefore, for the final analysis, the efficacy boundary (i.e., α_f) will be calculated using the rho family spending function with $\rho=1.5$, based on the planned number of 188 deaths at the first interim analysis, the actual number of 257 deaths at the second interim analysis and actual number of deaths at the final analysis. This will result in a more conservative efficacy boundary than the one using actual numbers of deaths for all scenarios for the actual number of deaths at the final analysis, as shown in Table 8. The efficacy boundary α_f will be fixed and documented prior to database hard lock for the final analysis. A two-sided p-value $\leq \alpha_f$ will be required to declare a statistically significant improvement in OS at the final analysis.

Table 8 Scenarios of Efficacy Boundary at Final Analysis

Actual Number of Deaths at Final Analysis	Two-Sided P-value Scale Efficacy Boundary at Final Analysis	
Based on 188 Planned Deaths at IA1, 257 Actual Deaths at IA2 and Actual Number of Deaths at Final Analysis	Based on 205 Actual Deaths at IA1, 257 Actual Deaths at IA2 and Actual Number of Deaths at Final Analysis	

Actual Number of Deaths at Final Analysis	Two-Sided P-value Scale Efficacy Boundary at Final Analysis	
	Based on 188 Planned Deaths at IA1, 257 Actual Deaths at IA2 and Actual Number of Deaths at Final Analysis	Based on 205 Actual Deaths at IA1, 257 Actual Deaths at IA2 and Actual Number of Deaths at Final Analysis
406	0.0354	0.0355
407	0.0354	0.0355
408	0.0355	0.0356
409	0.0355	0.0356
410	0.0356	0.0357
411	0.0356	0.0357
412	0.0356	0.0358
413	0.0357	0.0358
414	0.0357	0.0358
415	0.0358	0.0359
416	0.0358	0.0359
417	0.0358	0.0360

IA = Interim Analysis. Efficacy boundaries computed using EAST version 6.5.

7.5 Multiple Comparisons/Multiplicity

For the primary analysis the Type I error is controlled at $\alpha = 0.05$ (2-sided) over the 2 planned interim analyses and final analysis. Mathematical and simulation-based demonstration of type I error control is provided in Appendix 5. For the secondary endpoints the study-wise Type I error will be controlled using a sequential hierarchical approach as explained in Section 8.6.

7.6 Use of an “Efficacy Subset” of Patients

Patients in the mITT population who do not have major protocol deviations that may affect the efficacy evaluation, will form the Per Protocol (PP) Population. Major protocol deviations resulting in a patient being excluded from the PP population are defined in Section 8.3.3

Excluding patients who have major protocol deviations will likely decrease the variability in treatment response.

7.7 Examination of Subgroups

Primary and secondary efficacy endpoints will be summarized by the following subgroups:

- Stratification factors
 - HCC status (unilobar vs. bilobar disease)

- Region (North America and Europe vs Asia)
- ECOG performance status (0 vs 1) at baseline
- Presence or absence of branch PVT at baseline

Note: stratification factors according to the master file with any incorrect values at randomization replaced with the corrected value from the eCRF will be used.

Patients randomized prior to the stratification change to replace HCC status with Region will have their Region covariate assigned programmatically based on site. Patients randomized after the stratification change to replace HCC status with Region will have their HCC status covariate assigned based on the eCRF collected HCC status.

- Age group (≥ 18 to < 65 years, ≥ 65 to < 75 years, and ≥ 75 years)
- Gender
- Race (White or Caucasian, Black or African American, Asian, Other [Native Hawaiian or other Pacific Islander or Native American or Alaska Native or Other])
- US and non-US region
- Duration from date of initial diagnosis of HCC to randomization (< 6 months, ≥ 6 months)
- Tumor replacement (as percentage of total liver volume) at baseline by blinded central review ($< 20\%$ and $\geq 20\%$)
- Extrahepatic disease at baseline (yes or no)
- Child-Pugh class (A5, A6, B7) at baseline
- BCLC stage (B or C) at baseline
- HCC etiology, separately for two categorizations defined in Section 7.2
- Prior oncologic treatment for HCC (yes or no)
- Bilirubin (< 1 mg/dL or ≥ 1 mg/dL) at baseline
- ALBI score (1 vs 2 and 3) at baseline
- AFP (< 200 ng/mL or ≥ 200 ng/mL) at baseline
- Maximum lesion size at baseline, defined as the longest diameter of largest target lesion at baseline according to RECIST 1.1 by investigator assessment (< 7 cm or ≥ 7 cm)
- Number of lesions at baseline (< 3 lesions, 3-5 lesions, 6-10 lesions, > 10 lesions) by blinded central review

AEs will be summarized by the following subgroups:

- Age group (≥ 18 to < 65 years, ≥ 65 to < 75 years, and ≥ 75 years)
- Gender

- Race (White or Caucasian, Black or African American, Asian, Other [Native Hawaiian or other Pacific Islander or Native American or Alaska Native or Other])
- Region (North America, Europe, Asia)
- US and non-US region
- BCLC stage (B or C) at baseline
- Number of lesions at baseline (<3 lesions, 3-5 lesions, 6-10 lesions, >10 lesions) by blinded central review

8 STATISTICAL ANALYSIS

8.1 Disposition of Patients

The number of patients enrolled will be summarized by region (North America, Europe, Asia), country, and site. The number of patients randomized, and the number of patients treated with sorafenib only, TheraSphere and sorafenib, and TheraSphere only, prior to progression (i.e. prior to date of progression) as assessed by investigator according to RECIST 1.1, will be summarized. The number of untreated patients who discontinued from study will be summarized. The number of treated patients who discontinued from the study (treated and untreated) and the reasons for discontinuing from the study will also be summarized.

8.2 Protocol Deviations

Protocol deviations/violations will not be entered into the database. However, protocol deviations/violations will be identified and summarized within Labcorp's Clinical Department from which the Sponsor can make determinations. All protocol deviations/violations determinations will be made before the database is locked for statistical analysis.

8.3 Analysis Populations

8.3.1 *Modified Intent-to-Treat (mITT) Population*

All randomized patients who met the study eligibility criteria at randomization will form the modified Intent-to-Treat (mITT) Population and will be analyzed according to the treatment group to which they were randomized. This population will be used to analyze all efficacy endpoints.

8.3.2 *Safety Analysis (SA) Population*

All randomized patients who received study treatments at least once, prior to progression (i.e. prior to date of progression) as assessed by investigator according to RECIST 1.1, will form the Safety Population and will be analyzed according to the treatment actually

received prior to progression. Note that patients who received only TheraSphere (no sorafenib) prior to progression do not receive full treatment of either protocol-defined treatment group, so will be analyzed as a separate group in the safety population. This population will be used in all safety reporting and analysis.

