9.2.11 REVIEW ELIGIBILITY CRITERIA

Data detailing Demographic, Medical History, Physical Examination, ECOG Performance Status, Medication and Prior Oncologic Treatment, Tumor volume and Clinical Labs will be reviewed against eligibility criteria to determine eligibility. The determination will be recorded on the relevant case report form (eCRF).

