9.2.14 RANDOMIZATION (STUDY DAY 0)

Patients will be randomized 1:1 to study treatment, either the Control group or the Treatment group.

If a patient is determined to be eligible to participate in the trial, the study site will contact the central randomization office where randomization will be determined using assignment by a computer-generated randomization scheme. Upon randomization, each patient will be assigned a subject identity code consisting of the protocol number, the country code (e.g.01), the site number (e.g. 01) and a patient number (e.g. 001).

In order to create a balance between study groups, patients will be stratified at randomization based on the following:

- Region (North America and Europe versus Asia)
- ECOG performance status (0 vs 1)
- Presence or absence of branch portal vein thrombosis

Patients randomized to the Control group or the Treatment group who are unable to receive their planned study treatment will continue to be followed under their assigned study group for the purpose of the intent-to-treat analysis.

If a patient is found ineligible for the study, the patient will not be randomized and the reason for treatment ineligibility should be documented on the Screen Failure Log.

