15.0 MAJOR AND MINOR PROTOCOL DEVIATIONS

A major protocol deviation is defined as a divergence from the protocol that materially (a) reduces the quality or completeness of the data, (b) makes the Informed Consent Form inaccurate, or (c) impacts a subject's safety, rights, or welfare, example:

- Enrollment Violations
- Eligibility criteria deviations
- Inadequate informed consent Intentional repeated deviations from the protocol
- TheraSphere Administration Violations: TheraSphere treatment dose outside the range of 90-120 Gy \pm 10%
- Post-Treatment Violations: Administration of any liver-directed local regional therapy, except as specified by the protocol, following intra-hepatic progression.

A minor protocol deviation is defined as a divergence from the protocol that is without significant consequences to the patient and the study data. An example is missing a visit window because a patient is traveling.

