4.3 Blinding

This is an open label study and there is no blinding.

To maintain the integrity of the study results in this open label study, the following personnel who had access to the study data before database lock, were required to sign an “Aggregate Data Declaration Form” documenting their agreement to not produce or review aggregate summaries of efficacy and death data, including AEs with an outcome of death, separated by treatment arm:

- CRO (i.e. Labcorp) personnel who were not involved in preparing data summaries for the independent data monitoring committee (IDMC) meetings, and
- Sponsor personnel.

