5.1.1 Number of Study Centers and Subjects

In Version 4.1 of the protocol, dated May 20th 2014, the number of study centers increased from 40 to 105 and the number of patients changed from 400 to 390 with up to a maximum of 600 based on a sample size re-estimation.

In the current protocol (Version 6.1, dated November 29th 2016) the number of patients changed from 390 to 520 with the maximum based on a sample size re-estimation increased from 600 to 700 patients. Also, the analysis population for efficacy endpoints was changed from an intention to treat population, defined as all randomized patients, to a mITT population, defined as randomized patients who met the study eligibility criteria at randomization. This protocol amendment was implemented before the first interim analysis was conducted.

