8.6 Analysis of Efficacy Parameters

8.6.1 Analysis of Primary Efficacy Variable

The primary efficacy analysis is of OS. OS rates will be derived from the Kaplan-Meier estimates for each treatment group; 6, 12, 18 and 24 month OS rates will be presented, together with 95% confidence intervals (CIs). Quartiles will be presented and 95% CIs will also be calculated on the quartiles for each treatment group. A log-rank (two-sided) test, converted to a z-score, will be used to compare OS between the two treatment groups at an overall two-sided alpha level of 0.05. The two-sided alpha level of 0.05 will be adjusted over the 2 planned interim analyses and final analysis (as described in Sections 7.4 and 7.5). The HR and corresponding two-sided 95% CI for the treatment effect will be computed from a Cox proportional hazards model. Plots of the Kaplan-Meier curves will be provided for each treatment group. This analysis will be performed on the mITT population (primary analysis) and PP population (secondary analysis).

The assumption of proportional hazards used to compute the HR for OS will be assessed. Firstly, a plot of log[-log (estimated probability of event-free survival)] versus log(time) will be examined, with nonparallel curves for the 2 treatment groups indicating non-proportional hazards. Also, a time-dependent covariate Cox regression model (i.e. adding a treatment group by time interaction) will be fitted and if the time-dependent covariate has two-sided p-value <0.15 piecewise HRs over distinct time periods will be calculated.

For each patient that has not known to have died, OS will be censored at the time of last contact date known to be alive.

Note that any patient who is still on the study and has not withdrawn or died at the data cut-off (DCO) date for the final analysis will have an additional survival contact on the day of DCO or within 2 weeks of DCO date, with Patient Contact/Overall Survival log and/or Confirmation of Death eCRF page to be completed accordingly. If patients are confirmed to be alive or if the death date is after the DCO date these patients will be censored at the date of DCO.

All patients should be followed for OS, however, if a patient has not known to have died and not been followed for OS for any reason (i.e. no contact date known alive on Patient Contact/Overall Survival log eCRF page), censoring date will be defined as the latest among the following dates recorded on the eCRF:

- Adverse event start and end dates

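### Overall survival is analysed only in the mITT and PP sets: no analysis of all randomised patients is visible, and mITT exclusions in this open-label trial are not stated to be masked to arm or outcome

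*SAP*

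**What the plan says.** SAP 8.3.1 defines the efficacy set: "All randomized patients who met the study eligibility criteria at randomization will form the modified Intent-to-Treat (mITT) Population". For OS, SAP 8.6.1 states: "This analysis will be performed on the mITT population (primary analysis) and PP population (secondary analysis". Protocol 10.2.3 names the same two sets. The only sensitivity analysis that SAP 8.6.1 names for OS is poolability, which SAP 8.6.5 also runs on the mITT.

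An all-randomised set did exist. SAP 5.1.1 records that under protocol 6.1 "the analysis population for efficacy endpoints was changed from an intention to treat population, defined as all randomized patients, to a mITT population", and that this was done before the first interim analysis.

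On masking, SAP 4.3 says: "This is an open label study and there is no blinding". Sponsor staff, and CRO staff who do not prepare the data monitoring committee's summaries, sign "their agreement to not produce or review aggregate summaries of efficacy and death data" by arm.

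Other safeguards are present:
- Eligibility is judged on screening data and recorded (Protocol 9.1.1, 9.2.11).
- Eligibility deviations count as major (Protocol 15.0).
- Deviation decisions are due before database lock (SAP 8.2).
- Patients who cannot receive their treatment stay in their randomised group (SAP 4.2).
- Counts per analysis population are planned (Protocol 10.2.5).

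**The concern.** Protocol 9.2.14 says: "If a patient is found ineligible for the study, the patient will not be randomized". Anyone later removed from the mITT was therefore first recorded as eligible, and the removal revises that decision when the arm, and possibly the death, is already known. SAP 4.3 restricts aggregate summaries only. It does not stop the person judging one patient from knowing that patient's arm or vital status. SAP 8.3.1 sets the test as eligibility at randomisation but does not expressly exclude evidence obtained afterwards.

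The judgement has some room. Certain criteria are subjective, such as being at risk of liver or kidney failure. The synopsis and Protocol 8.1 differ on limits: INR below 2.0 against at most 2.0, tumour replacement above 70% against at least 70%, and resection more than 2 months before against at least 2 months. Several protocol versions and a separate German protocol also applied. Scrutiny after randomisation is unequal too, because only TheraSphere patients have work-up angiography and a MAA scan and must certify continued eligibility before administration (Protocol 9.2.15.1.1, 9.2.15.1.7).

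Exclusions that differ by arm and relate to prognosis would bias the primary HR. Counts per population could show that patients were removed, but not what the removal did to the HR.

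**Working it through.** **1. The plan's own figures reproduce.** The inputs are HR 0.754, 417 deaths, looks at 188, 250 and 417 deaths, and rho-family spending with rho = 1.5 (SAP 4.4, 7.4, Appendix 5). Solving the boundaries gives z = 2.429, 2.431 and 2.093, that is two-sided p of 0.0151, 0.0151 and 0.0363; the SAP has z = 2.430, 2.429 and 2.093. Power is 79.8% (stated 80%). Sample size is 468/0.9 = 520. No stated figure is wrong.

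**2. Patients at stake.** The plan assumes that 5% are wrongly randomised: 0.05 × 520 = 26, or 13 per arm. At the planned death rate this is 26 × 417/494 = 21.9 to 26 × 417/468 = 23.2 deaths, so an all-randomised analysis at the same date would have about 440 deaths.

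**3. Fragility at the boundary.** Suppose the mITT sits exactly on z = 2.093 with 417 deaths. The log-rank variance is about 417/4 = 104.25, so the score is 2.093 × √104.25 = 21.37. Restore 24 excluded deaths, *a* on TheraSphere and *b* on control: z = (21.37 − (a − b)/2) / √(441/4), with √(441/4) = 10.5.
- 12:12 gives 21.37/10.5 = 2.035, p = 0.042
- 16:8 gives 17.37/10.5 = 1.654, p = 0.098
- 18:6 gives 15.37/10.5 = 1.464, p = 0.143

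The splits are assumed. They show sensitivity, not expectation.

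**4. Simulation under a true HR of 1.** Assumptions: 520 patients 1:1, uniform accrual over 60 months, exponential survival with an eligible-control median of 10.7 months, 5% lost to follow-up, looks at 188, 250 and 417 mITT deaths, the SAP's boundaries and no event increase. Ineligible patients have 1.5, 2 or 3 times the hazard. There are 60,000 replicates per scenario (Monte Carlo SE 0.06 to 0.10 point). With no ineligible patients the one-sided error is 2.6%.

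| Excluded, TheraSphere vs control | mITT HR (hazard ×1.5 / 2 / 3) | One-sided error, all looks |
|---|---|---|
| about 12 vs 4 (90% / 30% detected) | 0.989 / 0.982 / 0.977 | 3.2 / 3.8 / 4.2% |
| about 10 vs 6 (75% / 48%) | 0.995 / 0.993 / 0.990 | 2.8 / 3.0 / 3.2% |
| 13 vs 13 (all detected) | 1.00 | 2.5% |
| about 4 vs 12 (30% / 90%) | 1.012 / 1.017 / 1.024 | 1.9 / 1.7 / 1.5% |
| stress: 8.3% ineligible, about 19.5 vs 6.5 | 0.982 / 0.972 / 0.962 | 3.9 / 4.8 / 5.9% |

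In every row the all-randomised analysis has HR 1.00 and error 2.4 to 2.7%.

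**5. Actual interim looks.** SAP 7.4 gives 205 and 257 deaths. With z bounds of 2.430, 2.410 and 2.099 and a final look at 417, the 12 vs 4 split gives 3.1, 3.6 and 4.2%, against 2.4 to 2.5% for all randomised.

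**The case against.** **The choice of set was not data-driven.** The change to mITT came before the first interim analysis. That is true, but it answers a different question: it supports the choice of set, not each individual exclusion.

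**An intent-to-treat analysis may exist.** The protocol synopsis and Protocol 9.2.14 still mention one, and a population is redacted in Protocol 10.2.1 and SAP 8.3.4. However, the visible SAP specifies no such analysis, SAP 4.2 gives the 9.2.14 sentence with mITT in its place, and SAP 8.6.1, which assigns the OS populations, is not redacted.

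**The masking gap is silence, not a shown defect.** Many criteria are numeric or dated, by-arm aggregates are barred, and decisions precede lock. This stands as mitigation. It does not cover patient-level knowledge of arm or death, and the step between soft close and hard lock in SAP 8.3.3 concerns the PP set.

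**The size rests on assumed inputs.** Only the 5% comes from the documents. Equal exclusion gives no bias, the reversed split is conservative, and the stress case exceeds the plan's 5%. The step 5 run ends at 417 deaths, although SAP 7.4 allows a cut-off on 30 April 2022 with fewer. All of this is right, and the figures should be read as illustration.

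**A second HR cannot separate bias from chance.** For 16 exclusions (about 14 deaths) the SE of the difference in log HR is roughly √(4/417 − 4/431) = 0.018. The 12 vs 4 shifts are 0.011, 0.018 and 0.023, or 0.6 to 1.3 SE. This also stands. The sensitivity analysis shows whether the conclusion depends on the exclusions; it is not a test for bias.

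**Follow-up of patients found ineligible is not assured.** Protocol 9.2.20 lets the investigator or sponsor end participation for any reason. That is a limit, although SAP 4.1 and 8.6.1 intend follow-up for everyone.

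**Conclusion.** The concern holds and should be fixed. In the visible text OS is analysed only in patients judged eligible and in their per-protocol subset. The existing safeguards cover timing and aggregate summaries, not the patient-level decision to exclude.

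The documents do not show that bias will occur, and its direction is unknown. Under the plan's 5%, assumed splits between 12 vs 4 and 4 vs 12, and assumed hazards of 1.5 to 3, the mITT HR under the null lies between 0.977 and 1.024, and one-sided error between 1.5% and 4.2%. That is small beside the design HR of 0.754, so it matters mainly if the result falls near the boundary.

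**What to change.** 1. In SAP 8.6.1, add a named sensitivity analysis beside the mITT primary: the OS log-rank test and Cox HR with 95% CI in all randomised patients, as randomised, at the same data cut-off.
2. In SAP 8.3.1, state that mITT exclusions rest only on data dated on or before randomisation, and are decided before hard lock by existing staff masked to the patient's arm and outcome.
3. Extend the population counts of Protocol 10.2.5 to show mITT exclusions by arm with the criterion failed.

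The cost is SAP wording, one extra run and a small masked review of suspected exclusions. No new data collection is planned for, the mITT stays primary and no alpha is spent. If lock has passed, items 1 and 3 can still be done.

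Precision changes little. At HR 0.754 with 5% ineligible and all detected, simulated power over all looks (30,000 replicates, SE 0.2 point) for the all-randomised analysis is 0.3 to 1.7 points above the mITT if ineligible patients benefit equally. If they do not benefit at all, it is 1.3 to 1.5 points below, with the HR about 0.01 closer to 1.
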